### Aggressive Myeloproliferative Disorders

Complete remission (CR): The patient must be free of all symptoms or signs related to MPD and have a white blood cell count (WBC) between 1 and  $10 \times 10^9/L$  with no peripheral blood blasts, promyelocytes or myelocytes and normalization of bone marrow (<5% blasts in normocellular or hypercellular marrow) for at least 4 weeks; resolution of pretreatment cytopenias including Hgb  $\geq 12.0 \text{ gm/dl}$  ( $\geq 11.0 \text{ gm/dl}$  for females) without erythropoietin or transfusion support; ANC  $\geq 1.0 \times 10^9/L$  and platelet count  $>100 \times 10^9/L$  without support; and resolution of pretreatment hyperleukocytosis and/or thrombocytosis ( $>450 \times 10^9/L$ ).

Partial remission (PR): improvement in two or more of the following: 1) ANC increase of 100% up to  $>10^9/L$  for neutropenia and WBC count between 1 and  $10 \times 10^9/L$  with persistence of immature cells (blasts, progranulocytes, myelocytes); 2) increase in Hgb of 2 gm/dl if baseline value was  $<10 \text{ gm/dl}$  and a decrease in transfusion requirements by at least 50% (frequency and/or volume); 3) persistent thrombocytosis  $>450 \times 10^9/L$  but  $<50\%$  of pretreatment values; 4) reduction in bone marrow blasts to  $\leq 5\%$  if blasts were  $>10\%$  in normocellular or hypercellular marrow; and 5) reduction in splenomegaly and/or hepatomegaly by 50% of pretreatment dimensions.

These definitions are consistent with those published by Giles et al. (48).

### **MPDs Transformed to Acute Leukemias**

Complete remission (CR): The patient must be free of all symptoms related to leukemia and have a neutrophil count  $>1 \times 10^9/L$  and platelet count  $>100 \times 10^9/L$ , and normal marrow differential ( $<5\%$  blasts). Must have clearance of extramedullary disease (including splenomegaly).

Partial remission (PR): meets the above criteria with the exception that leukemic blasts in the bone marrow may range from 6-25%, or  $\geq 50\%$  decrease in bone marrow blasts. May have persistent splenomegaly.

Hematologic Improvement: As per PR but ANC  $<1 \times 10^9/L$  and platelet count  $<100 \times 10^9/L$ . May have persistent splenomegaly and/or hepatomegaly.

These definitions are consistent with Giles et al (48) and Cheson, et al (49).

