### 3. PATIENT SELECTION

#### 3.1 Pre-Registration Eligibility Criteria

3.1.1 Patient has or suspected to have one of the following:

- Newly diagnosed Acute Myeloid Leukemia (AML) associated with antecedent myeloproliferative disorder (Polycythermia Vera, Essential Thrombocythemia, Myelofibrosis, atypical Chronic Myeloid Leukemia, Chronic Myelomonocytic Leukemia and related undifferentiated myeloproliferative/myelodysplastic disorders)
- Relapsed/refractory AML associated with antecedent myeloproliferative disorder (Polycythermia Vera, Essential Thrombocythemia, Myelofibrosis, atypical Chronic Myeloid Leukemia , Chronic Myelomonocytic Leukemia and related undifferentiated myeloproliferative/myelodysplastic disorders) who have received two or fewer prior induction chemotherapy courses
- Accelerated phase myeloproliferative disorders per Zeider et al with two or fewer prior therapies.
  - For aggressive phase MPD (P. Vera, essential thrombocythemia, Ph-negative chronic myelogenous leukemia), one or more of the following criteria must be met: marrow blasts >5%, peripheral blood blasts plus progranulocytes > 10%, new onset or increasing myelofibrosis, new onset or > 25% increase in hepatomegaly or splenomegaly, new onset constitutional symptoms (fever, weight loss, spleni pain, bone pain). Zeider et al
  - For Chronic Myelomonocytic Leukemia (CMML), the following criteria must be met: 5-19% bone marrow blasts (aggressive) or  $\geq$  20% marrow blasts (transformation).

3.1.2 Bone marrow and/or peripheral blood specimens will be submitted for correlative studies as outlined in Section 9. Patients with a dry tap will still be eligible.

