### 5.3 Duration of Therapy

In the absence of treatment delays due to adverse event(s), treatment may continue for 4 cycles (total) or until one of the following criteria applies:

- Failure to meet response criteria of CR, CRi, PR or MR as defined by protocol
- Disease progression
- Intercurrent illness that prevents further administration of treatment
- Unacceptable adverse event(s)
- Patient decides to withdraw from the study
- General or specific changes in the patient's condition render the patient unacceptable for further treatment in the judgment of the investigator
- Patient non-compliance
- Pregnancy
  - All women of child bearing potential should be instructed to contact the investigator immediately if they suspect they might be pregnant (e.g., missed or late menstrual period) at any time during study participation.
  - The investigator must immediately notify CTEP in the event of a confirmed pregnancy in a patient participating in the study.
- Termination of the study by sponsor
- The drug manufacturer can no longer provide the study agent

The reason(s) for protocol therapy discontinuation, the reason(s) for study removal, and the corresponding dates must be documented in the Case Report Form (CRF).

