### Acute myeloid leukemia

The following definitions are consistent with those published by Cheson/Dohner et al for acute leukemia (47).

**Complete Remission (CR):** Bone marrow showing less than 5% leukemic blasts with normal maturation of all cell lines, an ANC of at least 1000/ $\mu$ L and a platelet count of 100,000/ $\mu$ L, absence of blast in peripheral blood, absence of identifiable leukemic cells in the bone marrow, clearance of disease-associated cytogenetic abnormalities, and clearance of any previously existing extramedullary disease. Repeat marrow confirmation 4-6 weeks following the marrow documenting CR is not required due to the need for continued treatment in CR.

**Complete Remission with Incomplete Recovery (CRI):** All CR criteria except for residual neutropenia (ANC < 1000/ $\mu$ L) or thrombocytopenia (platelets < 100,000/ $\mu$ L).

**Partial remission (PR):** The presence of trilineage hematopoiesis in the bone marrow with recovery of ANC and platelets to the above stated levels, but with 5 to 25% bone marrow blasts, AND at least 50% decrease in bone marrow blast percentage from baseline.

**Clinical improvement/Minor Response (MR):** Non-progressive disease with at least a 20% decrease in marrow blasts and/or a decrease in leukemia-related symptoms (e.g., fever, bone pain, splenic pain, transfusion requirements) and signs (decrease in extramedullary site of leukemia).

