### 13.3 Stratification Factors

At the time of randomization, we will stratify according to 1) marrow blast percentage (<20% vs.  $\geq 20\%$ ).

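### In MPDs transformed to acute leukemia, PR can be met on an absolute 6-25% marrow blast range with no fall from baseline, while the overlapping AML block requires a fall of at least 50%

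*Combined protocol and SAP*

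**What the plan says.** Section 11.1.3 gives separate response criteria by disease. In the block for MPDs transformed to acute leukemia, CR begins "The patient must be free of all symptoms related to leukemia and have a neutrophil count" above 1 x 10^9/L. It also requires platelets above 100 x 10^9/L, marrow blasts below 5% and clearance of extramedullary disease, including splenomegaly. PR keeps these conditions "with the exception that leukemic blasts in the bone marrow may range from 6-25%, or" there is at least a 50% "decrease in bone marrow blasts. May have persistent splenomegaly". Hematologic Improvement is defined by reference to PR, with lower counts.

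The AML block of the same section defines PR as recovered counts with 5-25% marrow blasts, "AND at least 50% decrease in bone marrow blast percentage from baseline". CRi and minor response (MR) are defined only in this AML block.

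Eligibility (3.1.1) includes "Newly diagnosed Acute Myeloid Leukemia (AML) associated with antecedent myeloproliferative disorder", and its relapsed or refractory counterpart. At randomization "we will stratify according to 1) marrow blast percentage", cut at 20% (13.3).

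PR is used in four places:
- It can start the duration-of-response clock (11.1.1).
- It is one of the response categories assigned to every patient (13.7.2).
- It is among the phase I criteria that 11.2 says will be reported.
- It is named in the continuation rules: section 5.3 lists "Failure to meet response criteria of CR, CRi, PR or MR as defined by protocol" as a reason to end treatment, and 6.1 allows a repeat cycle after PR.

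**The concern.** A response category should record change. Here one of two alternative routes to PR is a fixed range of blasts, and that range overlaps the level at which transformed patients are expected to enter. Stable marrow disease can then be labeled a partial remission.

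The order of categories is also disturbed. PR can be met with no fall in blasts, while the lower category, MR, calls for a 20% fall and/or fewer symptoms or signs.

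The second difficulty is overlap. AML derived from an MPD is both a transformed MPD and an AML, and the two blocks give it different PR rules. An assessor needs the AML block in any case to call CRi or MR. The same marrow can be a PR under one block and not under the other. Response is graded by the principal investigator and no placebo is described, so the choice of rule should not be left to the reader.

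At stake are the PR count under the phase I criteria and any duration of response that starts from such a PR.

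**Working it through.** The plan states no figure for PR, so there is nothing to reproduce. The check applies the two blast rules to the same patients.

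**Rules.** Let b be baseline and f follow-up marrow blasts, in percent.
- Transformed-MPD block: 6 <= f <= 25, **or** f <= 0.5b.
- AML block: 5 <= f <= 25, **and** f <= 0.5b.

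**Entry level.** Section 3.1.1 gives 20% or more explicitly only for transformation of CMML, which has its own response block. It gives no number for AML derived from other MPDs. For those patients 20% is inferred from the cut in 13.1 and 13.3. A lower true entry level would widen the problem, because unchanged blasts from 6% upward also satisfy the first alternative.

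**Step 1: highest whole-number follow-up value accepted.** Relative change is (f - b)/b.

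| Baseline | Unchanged value accepted, transformed block | Highest f, transformed block | Highest f, AML block |
|---|---|---|---|
| 20 | yes | 25 (+25.0%) | 10 (-50.0%) |
| 22 | yes | 25 (+13.6%) | 11 (-50.0%) |
| 25 | yes | 25 (0.0%) | 12 (-52.0%) |
| 26 | no | 25 (-3.8%) | 13 (-50.0%) |
| 30 | no | 25 (-16.7%) | 15 (-50.0%) |
| 40 | no | 25 (-37.5%) | 20 (-50.0%) |
| 50 | no | 25 (-50.0%) | 25 (-50.0%) |

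Under the transformed block every unchanged value from 20% to 25% qualifies, and so does a rise from 20% to 25%. Between 26% and 49% a fall of less than half is enough. The AML block accepts none of these.

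**Step 2: how often this could happen with no true change.** The documents give no baseline blast distribution, so four were assumed. Each patient has the same true blast percentage at both visits. Measured values are binomial counts from 200 or 500 cells, and a patient enters if the first measured value is 20% or more. Share meeting the blast part only:

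| Assumed true blasts | 200 cells | 500 cells |
|---|---|---|
| Even, 10-90% | 8.1% | 7.5% |
| Even, 10-60% | 14.1% | 13.0% |
| 20% plus exponential, mean 25 points | 16.1% | 16.2% |
| 20% plus exponential, mean 15 points | 25.0% | 25.4% |

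Repeat runs differ by about a point, giving a range of about 7-26%. Among patients entering at 20-25%, roughly 67-80% met the blast part. Under the AML rule the share was 0.02% or less in every case.

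**Step 3: from blast part to PR.** A full PR also needs no leukemia symptoms, neutrophils above 1 and platelets above 100 x 10^9/L, and no extramedullary disease except splenomegaly. The documents do not say how many patients with unchanged blasts would meet these, so the full PR share is lower than step 2 by an unknown amount.

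**The case against.** The strongest reply is that little depends on this category. PR is not in the primary endpoint. Section 13.5 specifies reporting by arm for CR/CRi and for toxicity, not for PR. No comparison of PR rates or of duration of response appears among the objectives or planned analyses. All of this stands.

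Section 11.2 also plans a second report under the MPN-AML consortium criteria, where the nearest category (ALR-P) needs a blast reduction of more than 50%. Unchanged disease would not count there. This limits the damage but leaves the first report as it is.

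The transformed block says it is consistent with published definitions, so its wording may be inherited. That does not settle a conflict between two blocks that cover the same patients.

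The effect on continued treatment is partly absorbed by MR, which 5.3 and 6.1 also admit. A non-progressing patient whose leukemia-related symptoms decreased may already qualify that way.

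Two further criticisms are tempting but should not be made:
- A reader might infer that blasts from 5% to under 6% fall into no category. From a baseline of 20% or more, that is a fall of more than 70% (1 - 6/20 = 0.70), so the alternative of a 50% fall makes it a PR.
- A reader might call a change from 80% to 40% a wrongly counted PR. The CMML block and ALR-P also accept roughly a halving of blasts without a 25% ceiling, so a ceiling is a matter of preference.

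**Conclusion.** The point holds in a limited form. As written, the transformed-MPD block lets unchanged blasts of 20-25%, or a rise within that band, satisfy the blast part of PR. The AML block would refuse the same patient, and nothing says which block applies to AML derived from an MPD. This follows from the text. The one inference is the 20% entry level outside CMML, and a lower level would make matters worse.

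The size is uncertain. The 7-26% range is for the blast part alone, rests on assumed blast distributions and a simple cell-count model, and is an upper figure for PR in each scenario. A reader might go on to quote a rate of false PRs. The documents do not support one, because they give neither the blast distribution nor the share of patients meeting the other conditions.

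A reader might also infer that the trial's main result is at risk. It is not: the CR/CRi test and the stated power of about 91% do not use PR. What is affected is the PR category under the phase I criteria and duration of response. It should be corrected before responses are graded.

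**What to change.** Reconcile the two blocks of section 11.1.3:
1. State which block governs AML derived from an MPD, including where CRi and MR are taken from for these patients.
2. For response reporting, do not let the 6-25% range count as PR without a decrease from baseline, as the AML block already requires. Carry the change into Hematologic Improvement, which is defined by reference to PR.
3. If comparability with phase I matters, also report PR under the present wording as a sensitivity summary.

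How the reconciled category feeds the continuation rules in 5.3 and 6.1 is for the sponsor to settle; those sections need to be read against the revised definition.

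The cost is a short wording change. It uses the baseline and recovery marrows already in the study calendar and needs no change to sample size or to the primary analysis. The reported PR rate may be slightly lower and less comparable with phase I, which the sensitivity summary addresses.

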### **Chronic Myelomonocytic Leukemia (CMML)**

The definitions below are consistent with those detailed by Cheson, et al (50).

Complete response is defined by bone marrow showing  $<5\%$  myeloblasts with normal trilineage maturation without dysplasia. When erythroid precursors constitute  $<50\%$  of marrow cells, the blast percentage is based on total nucleated cells; otherwise, the blast percentage is based on non-erythroid compartment. Peripheral blood criteria consist of Hemoglobin  $\geq 11$  gm/dl, ANC  $\geq 1 \times 10^9/L$ , Platelets  $\geq 100 \times 10^9/L$ , absence of peripheral blood blasts, all in the absence of transfusions and growth factors.

Partial response is defined by all of the above criteria with the exception of bone marrow blasts decreasing by  $>50\%$  from pretreatment levels and/or achievement of a less advanced MDS FAB classification.

Stable Disease is defined by failure to achieve PR but without progression for at least 2 months.

Progression is defined according to initial blast percentages:

For patients with  $<5\%$  blasts:  $\geq 50\%$  increase in blasts to  $>5\%$

For patients with 5-10% blasts:  $\geq 50\%$  increase in blasts to  $>10\%$

For patients with  $>10-20\%$  blasts:  $\geq 50\%$  increase in blasts to  $>20\%$

For patients with  $>20-30\%$  blasts:  $\geq 50\%$  increase in blasts to  $>30\%$

In addition, there must be  $\geq 1$  of the following criteria:  $\geq 50\%$  decrease from maximum response levels in granulocytes or platelets, a decrease in hemoglobin concentration by at least 2 gm/dl, or becoming transfusion dependent.

### Acute myeloid leukemia

The following definitions are consistent with those published by Cheson/Dohner et al for acute leukemia (47).

**Complete Remission (CR):** Bone marrow showing less than 5% leukemic blasts with normal maturation of all cell lines, an ANC of at least 1000/ $\mu$ L and a platelet count of 100,000/ $\mu$ L, absence of blast in peripheral blood, absence of identifiable leukemic cells in the bone marrow, clearance of disease-associated cytogenetic abnormalities, and clearance of any previously existing extramedullary disease. Repeat marrow confirmation 4-6 weeks following the marrow documenting CR is not required due to the need for continued treatment in CR.

**Complete Remission with Incomplete Recovery (CRI):** All CR criteria except for residual neutropenia (ANC < 1000/ $\mu$ L) or thrombocytopenia (platelets < 100,000/ $\mu$ L).

**Partial remission (PR):** The presence of trilineage hematopoiesis in the bone marrow with recovery of ANC and platelets to the above stated levels, but with 5 to 25% bone marrow blasts, AND at least 50% decrease in bone marrow blast percentage from baseline.

**Clinical improvement/Minor Response (MR):** Non-progressive disease with at least a 20% decrease in marrow blasts and/or a decrease in leukemia-related symptoms (e.g., fever, bone pain, splenic pain, transfusion requirements) and signs (decrease in extramedullary site of leukemia).

### **Treatment Failure (TF):**

- **Resistant Disease (RD).** Failure to achieve CR or CRI; only includes patients who survive  $\geq$  7 days following completion of initial treatment, with evidence of persistent leukemia by blood and/or bone marrow examination.
- **Death in Aplasia (DA).** Deaths occurring  $\geq$  7 days following completion of initial treatment while cytopenic without evidence of persistent leukemia.
- **Death from Indeterminate Cause (DIC).** Death occurring before completion of therapy or < 7 days following its completion, or deaths occurring  $\geq$  7 days following completion of initial therapy with no blasts in the blood but without bone marrow available.

**Relapse:** Bone marrow blasts  $\geq$  5%; or reappearance of blasts in the blood; or development of extramedullary disease.

## 11.2 Other Response Parameters

Response criteria typically applied to MPN patients with acute leukemic transformation fails to capture meaningful clinical responses per the Cheson criteria(see below). A recent publication by the post-Myeloproliferative Neoplasm Acute Myeloid Leukemia Consortium describes revised response criteria per Table 1 below. As these response criteria have yet to be validated in a clinical trial, we intend to report responses both as criteria used in our phase I study(above) and as assessed by the proposed criteria by the MPN-AML consortium. These criteria are not to be

applied for CMML patients. A separate working group has developed revised response criteria for MDS/MPN including CMML which we will use as a secondary assessment for CMML patients per Table 2 below.

Table 1.  
 Myeloproliferative neoplasm in blast phase (MPN-BP) response categories.

Complete molecular response (CMR)	
Description	Complete remission of both leukemia and MPN without detectable molecular markers associated with either leukemia or MPN
Hematologic profile	
ANC > 1000
 
Hemoglobin > 10 g/dL
 
Platelets > 100 × 10^9/L
 
Absence of leukoerythroblastosisa

Spleen	Non-palpable
Bone marrow	
Cellularity appropriate for age
 
Resolution of abnormal morphology
 
Blasts ≤ 5%b
 
≤Grade 1 marrow fibrosis

Cytogenetics	Normal karyotype c
Molecular markers	Loss of any previously documented markers associated with either the leukemic or MPN clone d
Complete cytogenetic response (CCR)	
Description	Complete remission of both leukemia and MPN with detectable molecular markers associated with either leukemia or MPN
Hematologic profile	
ANC > 1000
 
Hemoglobin > 10 g/dL
 
Platelets > 100 × 10^9/L
 
Absence of leukoerythroblastosisa

Spleen	Non-palpable
Bone marrow	
Cellularity appropriate for age
 
Resolution of abnormal morphology
 
Blasts ≤ 5%b
 
≤Grade 1 marrow fibrosis

Cytogenetics	Normal karyotype c
Molecular markers	Residual expression of MPN/leukemia associated gene mutations (e.g. JAK2V617F, MPL515L/K) d
Acute leukemia response-complete (ALR-C)	
Description	Complete remission of leukemia with residual MPN features
Hematologic profile	Absence of blasts a
Spleen	<25% increase in spleen size by palpation or imaging if baseline spleen <10 cm or <50% if baseline spleen ≥10 cm

Bone marrow	Blasts $\leq$ 5% b
Cytogenetics	Loss of cytogenetic abnormality associated with leukemic clone, may have persistent abnormality associated with MPN
Molecular markers	Loss of any previously identified markers in leukemic clone, may have persistent molecular markers associated with MPN d
Acute leukemia response-partial (ALR-P)	
Description	Decrease in leukemic burden but without resolution of peripheral blood or bone marrow blasts and residual MPN features
Hematologic profile	>50% reduction in blasts
Spleen	<25% increase in spleen size by palpation or imaging if baseline spleen <10 cm or <50% if baseline spleen $\geq$ 10 cm
Bone marrow	>50% reduction in blasts
Cytogenetics	No new abnormalities
Molecular markers	No new abnormalities
Stable disease (SD)	
Description	Failure to achieve at least LR-P, but no evidence of progression for at least 8 weeks.
Progressive disease (PD)	
Description	Progression of leukemia and/or background MPN
Hematologic profile	For patients with 10-20% blasts: $\geq$ 50% increase to >20% blasts  For patients with >20% blasts: $\geq$ 50% increase to >30% blasts
Spleen	>25% increase in spleen size by palpation or imaging if baseline spleen <10 cm and >50% if baseline spleen $\geq$ 10 cm
Bone marrow	For patients with 5-10% blasts: $\geq$ 50% increase to >10% blasts  For patients with 10-20% blasts: $\geq$ 50% increase to >20% blasts  For patients with >20% blasts: $\geq$ 50% increase to >30% blasts
Cytogenetics	Does not apply
Molecular markers	Does not apply

a

Absence of peripheral blood blasts by morphologic review of the peripheral smear on two occasions separated by at least 2 weeks.

b

Blast percentage can be assessed by morphologic review of aspirate and in cases of inaspirate marrows, immunohistochemical staining of the marrow for CD34+, CD117+ is acceptable.

c

Normal karyotype by conventional cytogenetics in peripheral blood or bone marrow aspirate, if a cytogenetic abnormality is detected prior to treatment it must not be identified at time of assessment; if an abnormality is detected at baseline by FISH it must be absent by FISH at time of assessment.

d

Absence or loss of evidence of mRNA transcript by quantitative PCR assay performed in a validated laboratory, this will also include any exploratory biomarkers determined to be positive prior to therapy.

